#### Part 1: Demonstrate the reliability of remote pulmonary function testing, performed via telemedicine, for monitoring respiratory function in patients with amyotrophic lateral sclerosis (ALS)

*Primary Hypothesis:* There is no difference in the results of PFT and rPFT for respiratory assessment of FVC and MIP.

*Secondary Hypothesis:* The respiratory therapist, patient, and caregiver will express confidence in conducting the rPFT, as determined by surveys of procedure acceptance.

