### 1.2 Primary Study Endpoints

Part 1: The primary endpoint is completion of a standard PFT and an experimental rPFT during a single clinic appointment. At the endpoint, study outcomes will include:

- 1) The best FVC and MIP results from that visit's PFT
- 2) The best FVC and MIP results from that visit's rPFT
- 3) Survey responses from study participants.

Part 2: The primary endpoint for each person in the study is the completion of the fifth clinical visit, during which the control arm should have complete data for the following outcomes:

- 1) The results of five PFT administrations at 3 month intervals
- 2) Patient and caregiver monthly surveys

In addition, the experimental group will have engaged in eight additional guided rPFT assessments with the respiratory therapist over the telemedicine interface.

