### **3.2 Exclusion Criteria**

#### Part 1

Patients:

- 1) Cognitive impairment, as judged by the ALS clinic neurologist, that prevents participation in the study.
- 2) ALS Functional Rating Scale (ALSFRS-R) [Cedarbaum1999] score on day of screening of less than or equal to 2 on all of the items for speech, swallowing, and salivation. These items are indicators of bulbar dysfunction, which limits the reliability of PFT administration.

Caregivers: None

Controls: None

Respiratory Therapists: None

Part 2 imposes additional exclusion criteria for patients only.

Patients:

- 3) Use of NIV or diaphragm pacer at time of obtaining informed consent.
- 4) FVC  $\leq$ 50% predicted or MIP  $>$  -60 cm H2O.

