The Air Smart Spirometer works with iPhone and connects via its cable to the headphone input jack. The Air Smart Spirometer has a built-in battery designed to function for at least 2 years or 1 000 single tests. When the battery is drained, dispose of the device as electronic waste. The Air Smart Spirometer is designed to work with disposable and single use FlowMir® turbines. When performing a spirometry test, the user exhales into the turbine. The airflow generated sets a rotor in motion. The Air Smart Spirometer registers the speed of the spinning rotor, converts it and transfers the data to the smartphone with the Air Smart Spirometer app.”

2) GiO 4 Digital Pressure Gauge, Respiralogs

The following information is paraphrased from the user manual, which is included in the “devices” page of the protocol.

“GiO Pressure Gauge is a high accuracy digital gauge that displays pressure measurement in both analog bar and digital reading. The GiO Gauge can be used in various settings and has a wide range of

applications in both medical and non-medical fields. GiO Digital Pressure Gauge is designed to detect and display pressure reading to a high degree of accuracy. This means it may also be sensitive to changes in pressure and is so fast in responding to the changes that you may find it difficult to determine the reading you would like to record. The P&H or Peak and Hold function is a design that captures and holds the display of peak pressure reading. The GiO 4 measures pressures from -60 cm H2O to 0 cm H2O."

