During each rPFT administration, the respiratory therapist will guide the patient and caregiver through three valid maneuvers of the FVC and MIP tests. The therapist informs the caregiver to prepare the spirometer by connecting it to the tablet and opening the associated application. The patient is told to sit as upright as possible for the measurement of FVC. They will be told that to do this they will 1) inhale maximally, 2) exhale as hard and fast as possible, and 3) continue to exhale until indicated by the therapist. The therapist will also demonstrate this procedure to the patient. The caregiver applies nose clips to block airflow through the nose, holds the turbine of the spirometer to the patient's mouth and performs three repetitions of this sequence, with periods of relaxation between testings. Testing is repeated further until the therapist is satisfied with three valid maneuvers. The application on the tablet computes the FVC and percentage predicted value using the NHANES III criteria [Hankinson1999]. The largest FVC from a valid run is recorded.

To perform the MIP test, the therapist instructs the patient to breathe normally. The caregiver turns on the GiO pressure meter and attaches the mouthpiece, which is placed in the mouth of the patient. The patient is told they will be asked to draw breath in as quickly and powerfully as possible, for at least one second. The therapist tells the caregiver to place a finger over the valve outlet so that no air flows through the mouthpiece during inhalation. Nose clips will be used. As the therapist instructs, the patient performs three repetitions of this task, noting the reading each time. The maximal negative pressure from a valid run is recorded.

Each piece of reusable equipment will be labeled with an identification number. A log of all loaned materials will be maintained by the researchers. This log, included in the supporting documents, will be maintained on REDCap. Before delivery of the system to the study participant, the each piece of equipment will be inspected and tested. This study will not collect prior medical therapy relevant to the use of the device. There are no restrictions on medicines or therapies used by the participants in this study.

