## **8.0 Subject Numbers and Statistical Plan**

### **8.1 Number of Subjects**

Approximately (but no more than) 103. We will enroll 40 patient/caregiver teams for Part 1 and 40 patient/caregiver teams for Part 2. Participants in the two studies may overlap. Up to 20 practice control participants may be recruited for Part 1. Up to three respiratory therapists will also be recruited for these studies.

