### **8.3 Statistical methods**

Part 1: The primary hypothesis is that there is no difference in the results of PFT and rPFT for respiratory assessment of FVC and MIP. We will use a paired sample t-test to determine if the mean test results are comparable between the standard and experimental treatments. We will conduct a qualitative analysis to determine whether the patient, caregiver, and therapist determine the rPFT to be an effective way to conduct tests of breathing function.

Part 2: The primary outcomes will be analyzed to determine if respiratory parameters are closer to the actionable threshold at NIV recommendation and whether QoL is better sustained at this point in individuals in the experimental group. This will be done using a non-parametric two sample test of means, the Wilcoxon-Mann-Whitney rank sum test.

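### Part 1: the remote pressure meter ends at -60 cm H2O and no rule covers readings at that limit, so the paired test on MIP may reflect meter range rather than remote testing

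*Combined protocol and SAP*

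**What the plan says.** All references are to the combined protocol and SAP.

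- Section 1.1 gives the Part 1 aim as "Demonstrate the reliability of remote pulmonary function testing, performed via telemedicine, for monitoring respiratory function". The primary hypothesis is "There is no difference in the results of PFT and rPFT for respiratory assessment of FVC and MIP".
- Section 1.2 takes the best value of the visit from each method, including "The best FVC and MIP results from that visit's rPFT".
- Section 7.1 describes the remote meter: "The GiO 4 measures pressures from -60 cm H 2 O to 0 cm H 2 O". For the MIP manoeuvre, "The maximal negative pressure from a valid run is recorded".
- Section 8.3 gives the analysis: "We will use a paired sample t-test to determine if the mean test results are comparable between the standard and experimental treatments".
- Section 3.2 places the MIP limit among criteria that apply to Part 2 only: "Part 2 imposes additional exclusion criteria for patients only". A patient who qualifies for Part 2 has a MIP of -60 or stronger.
- Section 8.1 sets 40 patient/caregiver teams for Part 1 and adds: "Participants in the two studies may overlap".

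Sections 7.1, 7.2 and 8.3 contain no rule for a remote reading at or beyond -60. The documents do not state the range of the clinic MIP device, or what the remote meter shows beyond its limit.

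**The concern.** MIP is one of the two measures in the Part 1 primary hypothesis. The value analysed is the strongest of the visit, which is the one most likely to reach the end of the meter's scale. Nothing keeps stronger patients out of Part 1, and anyone who also qualifies for Part 2 is at or past the limit.

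Suppose the clinic device reads further and the remote meter stops. A patient at -85 in clinic then contributes a 25 cm H2O difference that has nothing to do with testing at a distance. Such differences all point the same way (remote weaker). A rejection could therefore come from meter range alone. If the remote test truly reads stronger, the same shift works against that difference and can cancel or reverse it. The planned output, a paired test on means, would not show which had happened.

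**Working it through.** **No figure to reproduce.** Section 8.2 bases its power on FVC decline and quality of life. It gives no MIP mean, SD or retest error, and no power for Part 1. The calculation below shows the mechanism and its possible size. It does not estimate what this trial will see.

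**Inputs.** From the documents: 40 pairs (8.1), paired t-test (8.3), remote limit 60 (7.1; pressures written as positive strengths). Assumed: two-sided 5%; strength Normal with mean μ = 30, 40, 50 or 60 and SD 20 or 30, floored at 0; independent retest error of SD s = 6, 10 or 15 on each device; clinic device unlimited; remote meter holds at 60. Each setting was simulated 20,000 times.

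**Average shift with no true difference.** A single reading has SD S = √(SD² + s²). With z = (60 − μ)/S, the mean remote deficit is S·φ(z) − (60 − μ)·[1 − Φ(z)], ignoring the floor at 0.

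- Example, μ = 60, SD 20, s = 6: S = √436 = 20.9, z = 0, deficit = 20.9 × 0.399 = 8.3.
- Example, μ = 30, SD 20, s = 6: z = 30/20.9 = 1.44, deficit = 20.9 × 0.142 − 30 × 0.075 = 0.7.

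| Mean strength | Readings over range, 1 − Φ(z) | Mean deficit, cm H2O | Rejection, no true difference |
|---|---|---|---|
| 30 | 8-19% | 0.7-3.4 | 7-28% |
| 40 | 17-28% | 1.9-5.7 | 15-62% |
| 50 | 32-38% | 4.3-9.0 | 41-93% |
| 60 | 50% | 8.3-13.4 | 84-100% |

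**By number of the 40 patients over range** (assumed mean excess 10-30 cm H2O): 4-6% with 1, 5-7% with 2, 7-19% with 4, 18-89% with 10 and 54-100% with 20.

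**Masking.** Let the remote test truly read 5 cm H2O stronger, with s = 6. Without a limit the test rejects about 95% of the time. With the meter held at 60, the mean difference is 5 minus the deficit computed at μ + 5.

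| Mean strength | Mean difference seen (true +5) | Rejection |
|---|---|---|
| 30 | +1.4 to +3.8 | 16-73% |
| 40 | -1.1 to +2.1 | 6-27% |
| 50 | -4.9 to -1.1 | 6-38% |
| 60 | -9.9 to -6.1 | 73-90% |

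At means 50 and 60 the average difference has the wrong sign. Most rejections at mean 60 would report the remote test as weaker when it is stronger.

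**Both readings cut at 60.** With equal retest error and no true difference, rejection is about 5% throughout. With unequal error it is not: SD 6 against 10 gives about 5-7%, and SD 6 against 15 gives about 6-15%, worst at mean 60. The cut also shrinks a real difference. At mean 60 and s = 6, a true 5 appears as 2.3-2.7, and power is about 69-78% instead of 95%.

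**Over-range remote readings dropped.** On the same grid, 8-50% of pairs are lost and rejection is still 5-34%. Treating them as missing is not a remedy.

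**The case against.** *The result depends on two facts that are not in view.* False rejection needs a clinic device that reads past -60 and a remote meter that stops there. The device manual sits elsewhere in the submission and may describe the display. This stands, and the point is conditional for that reason. A manual's description of the display would still not be a recording and analysis rule.

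*The size is wide open.* With no MIP distribution in the documents, the assumed range runs from nominal to 100%. This stands. Permission for patients to be in both parts makes over-range patients plausible but does not give their number.

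*A range-driven difference is a real difference.* The remote kit includes this meter, so a rejection would be true of the kit as delivered. That is correct. The fault is in interpretation: Part 1 is meant to support the reliability of testing at a distance, and a rejection caused by the end of a scale does not bear on that.

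*If both devices stop at -60 there is no problem.* This is only partly right. With equal retest error there is no false rejection, but a real difference is still shrunk.

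*The decision range is covered.* The meter spans the range weaker than -60, so MIP-based recommendations are unaffected. So are FVC, quality of life and the stated sample size. This stands.

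A reader might go further and infer that the Part 2 comparison is biased between arms. The documents do not support that. Section 8.3 does not say how closeness of MIP to the threshold is measured, so neither a bias nor its direction can be derived.

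**Conclusion.** The point holds for Part 1, on MIP only, and conditionally. The plan pairs a remote meter that ends at -60 with a test on mean differences, in patients with no MIP limit at entry, and has no rule for readings at the limit. If the clinic device reads further and the remote meter holds, the test can reject because of range alone, or can hide or reverse a true difference in the other direction. Size depends on how many of the 40 patients exceed the limit: negligible with one or two, and potentially decisive with ten or more. Every MIP mean, SD and retest error used here is an assumption, as is the two-sided 5% level.

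It would be too strong to say that the Part 1 MIP test will reject falsely or is invalid. The documents do not give the clinic device's range, the remote meter's over-range display or the number of patients affected.

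This should be fixed before the data are analysed, because choosing afterwards how to treat readings of -60 could decide the result. Confidence is medium.

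**What to change.** The change is to analysis and recording only.

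1. State the MIP range of both devices and what the remote meter shows beyond its limit.
2. Record remote readings at or beyond the limit as '-60 or stronger' (censored), not as a measured -60 and not as missing.
3. If the ranges differ, compare MIP with both readings cut at -60 and confine the conclusion to -60 to 0. Report the confidence interval, the number of censored pairs and the agreement on whether MIP is weaker than -60 (yes/no).
4. Add a censored-data estimate as a sensitivity analysis, for example bivariate normal with the remote value censored at -60.
5. State the limits of the cut: it shrinks a real difference, and it holds the 5% level only if the devices have similar retest error. If the remote meter proves to read past -60, the cut is not needed and would discard valid data.

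The cost is SAP wording and one recoding rule, with no change to visits, devices or sample size. Nothing is learned about agreement beyond -60, and power falls as shown above. The censored-data method recovered 4.5-5.4 for a true 5 (means 40-60, retest SD 6-10, 1,000 trials per setting), with 4-8% rejection under no difference. Its power at mean 60 and retest SD 6 was only 43-66%, so it supplements the cut and does not replace it.

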## 7.2 Study Procedures

### 7.2.1 Part 1

On or before the date scheduled for Study 1, a member of the research team who is not part of the ALS clinical team will describe the procedures and receive written informed consent from the patient and caregiver dyad, as well as the respiratory therapist. The participant team undergoes the initial in-person pulmonary function testing, followed 2-3 hours later at the end of the clinical visit by the rPFT. rPFT administration is described in Section 7.4.2. For roughly half of the enrolled participants, the order of assessments is reversed. Following the study procedures, the therapist and patient/caregiver dyad will complete a survey concerning the ease of use and confidence in the rPFT assessment.

Part 1 includes the recruitment of up to 20 practice control participants for validation of the study procedures. They will perform the same procedures as the patient and caregiver, in conjunction with the respiratory therapist.

### 7.2.2 Part 2

On or before the date scheduled for the start of the study, a member of the research team who is not part of the ALS clinical team will describe the procedures and receive written informed consent from the patient and caregiver dyad. The researcher will then collect demographic information for purposes of randomization to an arm of the study: age, gender, and time since symptom onset. The participant team will undergo the initial in-person pulmonary function testing as part of their clinical visit.

Month	0	1	2	3	4	5	6	7	8	9	10	11	12
Exp. Arm (n=20)	C+S PFT	S rPFT	S rPFT	S PFT									
Control Arm (n=20)	C+S PFT	S PFT	S PFT	S PFT									

**Table 1: Part 2 schedule. Participants will be enrolled at month zero, and randomized into a study arm depending on clinical characteristics of age, gender, and time since symptom onset (C). All participants attend clinic (indicated by gray shading) approximately every three months to have PFT administered by a respiratory therapist. Patients in the experimental group will conduct monthly rPFT assessments in the two interim months. Each month, all participants are required to complete the study survey (S).**

Following the initial visit (month 0), participants will undergo randomization. Those randomized to the experimental group will be shipped an rPFT kit and scheduled for monthly telemedicine appointments between clinic visits. On the dates of the telemedicine appointments, the respiratory therapist administers the study survey and conducts an rPFT from clinic with the patient in their home. This is repeated for the 2nd month. On the 3rd month, the participant dyad is seen by the therapist during their normal clinic visit. This pattern is repeated until the 5th clinical appointment (including the visit at month 0), resulting in 5 in-person assessments and 8 intermediate tele-assessments over the course of approximately 12 months. The control arm will receive standard assessments during regular ALS clinic appointments (Table 1), and be required to complete a study survey each month. Study procedures will be followed until the study endpoint at month 12, even if NIV is initiated during this period. The treating neurologist will make the decision to end the protocol early if the patient is unable to perform the procedures. The patient can also opt to end the study at any time.

The study survey is administered once a month for participants in both study arms and consists of four parts. The initial survey administered at month 0 will be completed with a researcher present. The remaining surveys will be completed online. If it coincides with administration of a PFT or rPFT, it will be administered first. It is designed to measure the impact of daytime breathlessness and sleepiness on QoL and consists of the following components.

- 1) Sleep Apnea Quality of Life Index (SAQLI) - part D [Flemons1998]. It is designed to assess quality of life pertaining to sleep disturbances, as well as the impact of treatment on QoL. It has been used as a sensitive measure of health-related QoL in ALS [Bourke2006, Jackson2001, Bourke2003].
- 2) Motor Neurone Disease Dsypnoea Rating Scale (MDRS) - subscale D [Dorman2007]. Dorman et al. described an ALS-specific assessment, the Motor Neurone Disease Dsypnoea Rating Scale (MDRS), as one with high construct validity and responsiveness. The dyspnea subscale (MDRS-D) of this tool has patients choose which activities of daily living they have experienced shortness of breath in the past two weeks and how severe the episode was [Dougan2000].
- 3) Short Form 36 (SF-36) [Ware1992]. This is a generic, coherent, and easily administered quality-of-life measures which has been shown to be sensitive for mental and physical health assessment in ALS [Bourke2006, Jackson2001, Bourke2003].
- 4) SAQLI parts E and F (NIV users only). These sections ask about problems that may have arisen due to NIV use and how respiratory symptoms may have been alleviated due to treatment during this period.

Each session concludes with recommendations from the therapist based on the results of respiratory tests. These can include behavioral modifications or recommendation for NIV. Recommendation of NIV is based on a measured FVC  $\leq$ 50% predicted or for dyspnea accompanied by MIP  $>$  -60 cm H2O. This recommendation will be reviewed by the ALS clinic neurologist. If the decision is made to initiate NIV, the ALS clinic physician will provide an order, and the ALS clinic nurse will arrange for initiation of in-home NIV via a third-party vendor according to usual standards of care.

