## **7.0 Study Design and Procedures**

### **7.1 Study Design**

Part 1: This is a self-controlled study where each participant will be administered a standard of care PFT for measurement of FVC and MIP, as well as an rPFT, separated by at least an hour, for measurement of experimental FVC and MIP. The rPFT is guided by a respiratory therapist in another room, utilizing the telemedicine interface of the Hersey ALS clinic and devices for measuring FVC and MIP (**Error! Reference source not found.**).

Part 2: This is a randomized controlled study to determine whether regular monitoring of respiratory function at monthly, rather than every 3-month intervals, over the course of a year, can lead to better

**Figure 2: (A) Image of the telemedicine interface used by the Hershey ALS clinic. (B) The rPFT toolkit. From left to right: The GiO 4 respiratory pressure meter and mouthpiece, smartphone running the spirometry application, and Air Smart Spirometer and turbine.**

patient outcomes. In the experimental group, standard FVC and MIP measurements obtained by the respiratory therapist in the ALS clinic every 3 months are supplemented with telemedicine-guided rPFT performed at monthly intervals (**Error! Reference source not found. 1**). Controls receive standard PFT assessments only. Patient outcomes, NIV recommendation, quality of life, and survival over one year, will be compared between experimental and control groups.

The researcher and respiratory therapist will be present either in person or virtually for all study sessions and will guide the patient and caregiver in the appropriate use of the equipment. Two devices are used to measure two aspects of respiratory function:

1) Air Smart Spirometer, Pond Healthcare Innovation AB

The following information is paraphrased from the user manual, which is included in the “devices” page of the protocol.

“Air Smart Spirometer is intended to measure the forced expiratory volume in 1 sec (FEV1) and the forced vital capacity (FVC) in a forced expiratory maneuver. These measures can be used for the detection, assessment and monitoring of certain lung diseases. The Air Smart Spirometer is intended to be used by:

- Healthcare professionals trained to perform spirometry tests on patients.
- Adults trained by healthcare professionals or through self-learning who understand how to perform a high quality spirometry test.

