### **8.2 Sample size determination**

Our sample size is predetermined based on our subjective ability to recruit patients within the time frame of the study. Power analysis was based on studies of FVC decline. Lo Coco et al., [LoCoco2006], showed that 50% of study participants dropped below 50% predicted FVC in one year. Given that our exclusion criteria for Part 2 will reject many of the 37% of individuals in their study who were "slow progressors," we estimate that 75% of patients enrolled in our study will meet the respiratory criteria to recommend NIV. This results in a sample size per arm of n=15, which provides 80% power to detect a difference in mean outcome between the two groups if the effect size is found to be 0.95.

Assuming a monthly change in FVC of  $3.5 \pm 3.4\%$  found by Schiffman et al. [Schiffman1993], we conducted 10,000 Monte-Carlo simulations of 40 participants declining at this rate for 12 months. Half were sampled once every three months, and half were sampled every month.  $80.6 \pm 6.3\%$  of simulated participants met the requirements for NIV recommendation, in roughly equal proportions across groups. The average FVC at recommendation was 47.0% predicted in the experimental group, and 43.4% predicted in the control group. The effect size of the difference in FVC between groups was  $.964 \pm .343$ . Similarly, the two measures of QoL obtained at NIV recommendation are powered with an 80% chance to detect improvement of quality of life in the experimental group if the effect size is also found to be 0.95. This corresponds to a mean score difference of 1.52 on the SAQLI, assuming a standard deviation of 1.6 [Flemons1998]. Although there is no published data on the standard deviation of MDRS-D scores, the range and format of questions is similar enough to estimate a comparable difference between groups is needed.

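### Part 1 does not say how test order is assigned and analyses it without a period term, so any order effect stays in the SD of the differences and, if the split is uneven, partly in the mean

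*Combined protocol and SAP*

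**What the plan says.** Section 7.1 describes Part 1 thus: "This is a self-controlled study where each participant will be administered a standard of care PFT for measurement of FVC and MIP". Each patient also has an rPFT, with the two tests "separated by at least an hour". Section 7.2.1 puts the in-person PFT first, "followed 2-3 hours later at the end of the clinical visit by the rPFT", and then adds: "For roughly half of the enrolled participants, the order of assessments is reversed". It does not say how the reversed patients are chosen, whether the split is fixed, or whether the order is recorded. Section 7.2.2 describes randomisation, but only to the Part 2 arms.

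The Part 1 hypothesis in section 1.1 is: "There is no difference in the results of PFT and rPFT for respiratory assessment of FVC and MIP". Section 8.3 tests it as follows: "We will use a paired sample t-test to determine if the mean test results are comparable between the standard and experimental treatments". No order, period or sequence term is mentioned. On numbers, section 8.1 says "We will enroll 40 patient/caregiver teams for Part 1 and 40 patient/caregiver teams for Part 2", and section 8.2 says "Our sample size is predetermined based on our subjective ability to recruit patients within the time frame of the study". No SD, margin, significance level or power is given for Part 1.

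**The concern.** When every patient is tested twice in one day and the order is switched for some, the difference between devices and the difference between first and second test have to be separated. An order effect is plausible here. Section 7.1 asks for repeated maximal efforts at each rPFT, with a therapist demonstrating the technique, and the standard PFT falls on the same visit. Patients may tire, or may do better at the second test because they have learned the manoeuvre.

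The plan recognises this by reversing the order, but does not carry it into the allocation or the analysis. The direction of the error matters. The hypothesis is one of no difference and has no equivalence margin, so a non-significant t-test would be read as support for the remote test. Anything that inflates the SD of the paired differences makes that result more likely.

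**Working it through.** **Inputs from the documents.** 40 patients (section 8.1), two tests each (7.1), order reversed for about half (7.2.1), paired t-test (8.3). There is no Part 1 power or precision figure to reproduce.

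**Assumptions.** Order effect p from 0 to 1.0 SD of the paired difference; normal errors; two-sided 5% test; all 40 patients complete both tests.

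**Model.** For patient i, let D_i = rPFT minus PFT = τ + p·s_i + e_i. Here τ is the device difference, s_i = +1 if the rPFT is second and −1 if it is first, p is the second-minus-first effect, and SD is that of e_i. Let n1 patients have the rPFT second and n2 have it first.

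**1. Even split (20/20).** The mean of D is τ + p(20 − 20)/40 = τ, so there is no bias. The sample SD of D is inflated by √(1 + (p/SD)² × 40/39):

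- p = 0.25 SD: √(1 + 0.0625 × 1.026) = 1.03
- p = 0.5 SD: √(1 + 0.25 × 1.026) = 1.12
- p = 1.0 SD: √(1 + 1 × 1.026) = 1.42

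**2. Effect on the test at 20/20.** Simulation, 100,000 runs per setting; power is for a true device difference of 0.45 SD.

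| p (in SD) | Type I error, paired t | Power, paired t | Power, period term |
|---|---|---|---|
| 0 | 0.050 | 0.79 | 0.79 |
| 0.25 | 0.043 | 0.78 | 0.79 |
| 0.5 | 0.029 | 0.72 | 0.79 |
| 1.0 | 0.006 | 0.49 | 0.79 |

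**3. Uneven split.** The bias of the unadjusted mean is p(n1 − n2)/40.

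- 22/18: p × 4/40 = 0.1p. Type I error is 0.045, 0.035 and 0.016 for p = 0.25, 0.5 and 1.0 SD; the extra variance outweighs the bias.
- 24/16: p × 8/40 = 0.2p. Type I error is 0.054, 0.062 and 0.066.

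Since the sign of p is unknown, this bias could hide a device difference or create one.

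**4. Order related to the patient.** Suppose the order effect is p1 in those tested with the rPFT second and p2 in those tested with it first. The sequence means are then τ + p1 and τ − p2. At 20/20 their average is τ + (p1 − p2)/2. This bias vanishes only if p1 = p2, and a period term does not remove it, because that term assumes a common p.

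**5. With a period term.** The estimate is the mean of the two sequence means. Its standard error is s√(1/n1 + 1/n2)/2, with s the pooled within-sequence SD on 38 df. At 20/20 this is s√0.1/2 = 0.158s, the same as s/√40, so only one degree of freedom is lost. In the simulations bias was zero to rounding and type I error 0.05 at both even and uneven splits. Power at 24/16 was 0.77 to 0.78.

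**The case against.** The strongest reply is that reversing the order is counterbalancing, the standard protection, and that it works. A common order effect cancels from the mean at an even split, and 22/18 leaves only a tenth of it. Each patient is their own control, so stable differences in severity drop out. The gap of hours between tests, the rest between efforts and the use of the best valid result all plausibly limit fatigue and learning. At p = 0.25 SD the period term gains about one point of power. All of this stands, and it is why the point is minor.

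A reader might infer more: that order is deliberately not randomised, that clinic staff pick it by schedule or by how tired the patient looks, or that fatigue and learning flow straight into the device comparison. The documents do not support these readings. They are silent on how order is assigned and describe no choice by staff. With the planned reversal, a common order effect does not bias the mean unless the split is uneven.

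Two further limits apply. The additive model fits MIP less well, because the remote gauge described in section 7.1 reads only from −60 to 0 cm H2O and cannot register a shift beyond that range. And a period term does not supply the missing equivalence margin; it makes the comparison cleaner but cannot by itself show agreement.

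What the reply does not answer is that cancellation in the mean leaves the variance inflated, that an approximate half does not secure an even split, and that an unstated rule gives no protection against the situation in step 4.

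**Conclusion.** The point holds in a limited form and is minor. Followed as written, the paired t-test leaves any order effect in the SD of the differences even at 20/20. It also leaves a fraction (n1 − n2)/40 of that effect in the mean when the split is uneven. Over the assumed range the power loss at 20/20 runs from negligible (0.79 to 0.78) to large (0.79 to 0.49), and it tilts the result towards no difference found. Bias from a patient-related choice of order is possible but cannot be sized, since the assignment rule is not given. All magnitudes depend on an order effect and an SD that the documents do not supply.

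**What to change.** - **Section 7.2.1:** assign order from a pre-generated, balanced 1:1 random list (20 patients per order), and record the order for each patient. Random assignment is what guards against order being linked to fatigue or learning.
- **Section 8.3:** replace the plain paired t-test with an estimate of the rPFT minus PFT difference, for FVC and for MIP, from a model with a period term (mean of the two sequence means, pooled within-sequence SD, 38 df).

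Both changes are needed: the list secures balance and removes selection into an order, and the period term removes the common order effect from the residual variance. The cost is an allocation list, one recorded field, a sentence in the analysis plan and one degree of freedom. No extra patients, visits or tests are required.
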